4.1.2 Method of assigning patients to treatment groups

Patient assignment to the treatment groups will be determined by IRT. Access to the randomisation code will be controlled and documented. All necessary instructions for using the IRT system will be described in a user guide/manual, a copy of which will be available in the ISF.

Patients have an equal chance of being randomized to DE or ASA with an allocation ratio of 1:1.

At Visit 2, patients will be randomized and receive study medication for the first time. If the patient is not randomized, a screen fail call will be made in the IRT System. When patients return for the next scheduled visit (see [Flow Chart](#)), unused medication will be returned by the subject. Trial drug will be supplied on a per visit basis. Supply will be managed by IRT.

All study drug dispensed and returned to patients should be recorded by Investigator/designee on the Investigational Medicinal Product Accountability Forms. These original forms will be retained and the site and a copy filed in TMF.

4.1.3 Selection of doses in the trial

The doses of DE selected for this trial are the same as those used in RE-LY, the Phase III trial for SPAF. In RE-LY, a dose of DE 110 mg b.i.d. was shown to be comparable to warfarin (INR level 2.0–3.0) for preventing strokes and SE, and superior when considering major bleeding risk with a relative risk reduction of 20% ([U09-3249-02](#)). Moreover, there was an approximately 60% reduction in intracranial hemorrhage with both dosages of DE.

The overarching goal related to this exposure level is to achieve superiority in efficacy over ASA with no clinically meaningful excess in bleeding with DE. To achieve this, the dosing instructions applied in this trial are intended to provide homogeneous exposure distribution among patients included into this trial. This means that patients at higher risk of bleeding (i.e. patients aged 75 years or older, or with moderate renal impairment) will receive the lower dose of 110 mg b.i.d. and will achieve an exposure comparable to those patients without these risk factors.

The average exposure across all patients (dabigatran trough levels) will range between the trough levels achieved with 110 mg b.i.d. (median of 66 ng/ml) in the RE-LY trial and the level obtained with 150 mg b.i.d. in RE-LY (median of 93 ng/ml): By utilizing the PK experience from RE-LY ([U09-3249-02](#)) and by considering patients characteristics such as age and renal function from a secondary stroke population included in the PROFESS study ([U08-3667-01](#)), PK modeling has shown that the dosing algorithm in this study will result in a median of plasma trough levels of approximately 77 ng/mL. This exposure is expected to provide superior efficacy over the antiplatelet agent ASA with a comparable low rate of intracranial hemorrhage and the overall ability to deliver an optimal balance of efficacy and safety across the population in the trial.

To obtain the targeted exposure, dabigatran dosing will be adjusted for age and renal function, as follows: Patients will be assigned to DE dose of 150 mg b.i.d., unless they are 75 years or older, or have a CrCl of ≥ 30 to < 50 ml/min, in which case they will receive DE 110 mg b.i.d.

Patients assigned to DE, who initially qualify to receive 150 mg b.i.d., will be down-titrated to 110 mg b.i.d. if their CrCl deteriorates to ≥ 30 - < 50 mL/min, if they experience a GI bleed, or the patient becomes 75 years old during the course of the trial. The patient will be

asked to return their 150 mg medication and receive 110 mg at an unscheduled visit as soon as possible if their titration is due to drop in CrCl or GI bleed. Patients who turn 75 years old during the trial will receive the 110 mg dose at their next scheduled visit. Patients will only have the option to change the dose once, i.e. there will be no up-titration from 110 to 150 mg b.i.d. if renal function recovers.

Using the characteristics of higher risk populations, modeling shows comparable exposure (median trough concentration of 89 ng/ml) in patients receiving DE 110 mg b.i.d. compared to patients without these risk factors receiving DE 150 mg b.i.d. (median trough concentration of 74 ng/ml) in this trial. Therefore it is concluded that dose adjustment to DE 110 mg b.i.d. may optimize the risk-benefit profile in patients at higher risk of bleeding.

The 100 mg dose of ASA was selected based upon recommendations in current guidelines and because this dosage is widely available and acceptable to most clinicians around the world. Patients assigned to ASA will not change their ASA dose during the course of the trial.

Because assignment of ASA vs. DE is blinded, all patients will have their DE down-titrated via IRT under the age, GI bleed or renal function conditions mentioned above. It will be unknown if the DE kits are active or placebo.

4.1.4 Drug assignment and administration of doses for each patient

Drug is dispensed by the Investigator, study coordinator, or pharmacist, depending on the study organization. IRT will be used to assign an appropriate active study drug and placebo to the patient. The site staff will be prompted to notify the IRT of all relevant information to identify patient as well as assign appropriate DE dose according to the algorithm (i.e. according to age, renal function and GI bleed that occurs during the course of the trial).

Study drug is dispensed every three months over the first year and every 6 months thereafter at regularly scheduled study visits (except the EOT and Final Visit). Study drug kits will contain enough supply to last until the next visit plus some overage.

Patients randomized to active treatment with DE will also receive an ASA placebo kit. Patients randomized to active treatment with ASA will also receive a DE placebo kit.

Patients will be instructed on the importance of taking both the active and placebo treatment because they will not know which one is active versus placebo.

Adjustments of DE dose can occur once per patient and will be managed within the IRT system.

Dabigatran etexilate capsules should be taken in the morning and in the evening, at the same time every day. The interval between doses should be as close to 12 hours as possible. If a dose of DE is not taken at the scheduled time, the dose should be taken as soon as possible on the same day; the missed dose should be skipped, if it cannot be taken at least 6 hours before the next scheduled dose. The next dose of DE should not be doubled to make up for a missed dose. If a dose of ASA or matching placebo is not taken at the scheduled time, the dose

should be taken as soon as possible on the same day; the missed dose should be skipped if it cannot be taken at the same day. For visits with pharmacokinetic trough sampling (Visit 1, Visit 3 and Visit 6 as outlined in the [Flow Chart](#)) patients should take that morning dose of trial medication at the study site (after the blood sample has been taken) to ensure the pharmacokinetic sample is taken at trough, 10:00-16:00 hours after the last drug intake and prior to the next drug intake.

Patients should be advised to take study medication with a full glass of water. Breaking or chewing of the tablets or capsules, or emptying the contents of the capsules is not permitted. The capsules and tablets should be swallowed as a whole and should not be dissolved in liquid. It is possible to take study medication with or without food. By taking study medication with food, dyspepsia-like side effects associated with DE may be reduced ([U13-3509-01](#)). If dyspeptic symptoms remain, the Investigator should consider adding a proton pump-inhibitor or H2-blocker to the concomitant therapy of the patient.

Start of study treatment following the qualifying event of ESUS:

The decision about starting study medication after qualifying stroke is at the discretion of the Investigator. In general, study medication should be started as early as possible under consideration of the severity of the stroke and after ensuring that intracranial hemorrhage has been excluded. Recommendations on the earliest possible time point to start study medication are provided in [Table 4.1.4: 1 \(P12-02400\)](#).

Table 4.1.4: 1 Recommendations on starting study medication after index event of stroke (mRS \leq 3 at time of randomization) and for reintroduction of study treatment after recurrent stroke (mRS \leq 3 at time of study medication restart)

Stroke Severity (at time of randomization / at time of study medication restart after recurrent stroke)	Earliest start of Study Medication after Stroke
Symptom resolution within 24 hours with evidence of brain damage by imaging	As soon as imaging has excluded a cerebral hemorrhage
Modified Rankin Scale = 1 or 2	3-5 days after most recent stroke onset ¹ Brain re-imaging is not required if starting study medication more than 10 days after index stroke.

Modified Rankin Scale = 3
 
Please take note:
 
This category includes patients with an initial Modified Rankin Scale of 4 at time of stroke, who have improved to a Modified Rankin Scale of 3.
 
Patients with Modified Rankin Scale of 4 at time of randomization are excluded.
 
Patients with Modified Rankin Scale of 4 cannot restart study medication unless their Modified Rankin Scale improves to 3.
	
5-7 days after most recent stroke onset¹
 
Brain re-imaging is not required if starting study medication more than 10 days after index stroke.

¹ If starting study medication within 10 days of most recent stroke in patients with mRS of 1, 2, or 3, re-imaging of the brain is required to rule out bleeding into the brain. Randomization in these patients should only occur after reimaging of the brain has been performed and eligibility has been confirmed. Hemorrhagic transformation of a primarily ischemic stroke may be included as per Investigator's judgment. Sporadic microbleeds may be included as per Investigator's judgment. As a general recommendation, a cerebral microbleed is considered to be in general \leq 5mm, but sometimes up to 10 mm, in greatest diameter on gradient recalled echo (GRE), or T2*, MRI sequences. Microbleeds are incidental findings that do not constitute an exclusion criterion. In patients with hemorrhagic transformation or microbleeds, the Investigator may choose to delay the start of study medication. Any blood visualized on a CT will be classified as a macrobleed. In patients with macrobleeds, study medication should not be started.

Treatment will continue until the end of the study if there is no reason to stop treatment earlier. The date of last dose of study drug will be recorded on the eCRF.

Secondary stroke prevention treatment for patients after the completion of this trial is at the discretion of the Investigator or other treating physician.

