10. Standard safety lab panel to be analyzed by central lab (hematology and chemistry, including renal function and liver function tests (LFTs) will be collected). Lab testing is specified in [Section 5.2.3](#). Local labs (within 14 days prior to randomisation) can be used to verify eligibility (in addition to collection of central labs) where it is necessary to avoid delaying the initiation of study drug. Refer to [Section 5.2.3](#) for calculation of Creatinine Clearance (CrCl) and [Section 4.1.3](#) for information about dose changes based upon CrCl value. Central labs must also be collected from all patients to provide a baseline for the study. This should preferably occur at Visit 1, however, it can alternatively be collected at Visit 2 prior to first study drug intake. Follow-up safety labs do not need to be drawn on the actual day of the visit. They may be drawn earlier as long as it is within the visit time window.

17. National Institutes of Health Stroke Scale (NIHSS) is a tool used to evaluate impairment after a stroke outlined in [Section 5.3.2](#). This neurological assessment is to be completed for qualifying stroke only. NIHSS is not required after recurrent stroke.
18. Restricted medications are listed in [Section 4.2.2](#).
19. Recommendations on timing of starting study medication after index stroke and recurrent stroke are provided in [Table 4.1.4:1](#). Patients with mRS of 1,2 or 3 AND initiating study medication within 10 days of index event require repeat imaging of the brain to rule out bleeding into the brain (per [Exclusion #6](#)). For index strokes, this repeat imaging must occur prior to randomization. This repeat imaging done specifically to initiate study drug is required per protocol in select patients. Conversely, brain imaging for initial evaluation of index and recurrent strokes should occur according to local clinical practice (i.e. not done specifically for this trial).
20. Concomitant medication will include medications of interest taken during the 30 days prior to randomization plus those given as treatment for index stroke.
21. For endpoint events which require adjudication as per [Section 3.1.1.4.](#), copies of relevant source documentation (e.g. imaging reports) should be collected and submitted.

TABLE OF CONTENTS

TITLE PAGE	1
CLINICAL TRIAL PROTOCOL SYNOPSIS	2
FLOW CHART	6
TABLE OF CONTENTS	10
ABBREVIATIONS	14
1. INTRODUCTION.....	18
1.1 MEDICAL BACKGROUND	18
1.2 DRUG PROFILE	20

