For hemorrhagic stroke or other intracranial bleeding, consultation with a coagulation expert and a neurosurgeon is recommended. See “Major Bleeds” earlier in this section for details relating to how to manage bleeding.

In case of recurrent stroke during the trial, it is at the Investigator's discretion whether study medication will be restarted or whether the patients will be switched to appropriate standard of care antithrombotic treatment.

Reintroduction of study treatment following a stroke (i.e. after recurrent stroke)

The decision about when to restart study medication following a recurrent stroke is at the discretion of the Investigator (with the exception of strokes with mRS of 4 or higher, where restart is not allowed, unless the patient improves to a mRS of 3). [Table 4.1.4: 1](#) shows recommendations ([P12-02400](#)) on the earliest possible time point to start study medication. These recommendations in [Table 4.1.4: 1](#) also apply to restarting study medication after recurrent stroke. Cerebral hemorrhage must be excluded before study drug is restarted. If restarting study medication within 10 days of stroke in patients with mRS of 1, 2 or 3, re-imaging is required to rule out bleeding into the brain (for details see footnote of [Table 4.1.4: 1](#)).

Acute Coronary Syndrome (ACS)

In patients with documented or suspected ACS, study drug should be temporarily discontinued.

Medication Management of ACS

ASA, clopidogrel and glycoprotein IIb/IIIa inhibitors may be administered according to usual clinical practice. However, the concomitant use of these treatments with study medication may increase the risk of bleeding.

For the use of heparins (UFH or LMWH) or other anticoagulants to manage ACS, the following guidance is provided for consideration:

Unfractionated or low-molecular-weight heparin should be withheld until the aPTT is less than 1.5 x ULN (upper limit of normal):

- If the aPTT is between 1.2 and 1.5 x ULN, UF heparin may be commenced preferably without an intravenous loading dose and LMWH may be commenced at the usual therapeutic dose
- If the aPTT is above 1.5 times the ULN, it should be repeated every four hours until it falls below this level, after which heparin or other anticoagulation can be commenced.

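### Table 4.1.4: 1 times its re-imaging waiver from the index stroke in the mRS 1-2 and mRS 3 cells, although the table also governs restart after a recurrent stroke

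*Protocol*

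**What the plan says.** The title of Table 4.1.4: 1 (Protocol section 4.1.4) covers starting study drug after the index stroke "and for reintroduction of study treatment after recurrent stroke". Section 4.2.1, under the heading on reintroducing treatment after a stroke, confirms that the table's recommendations "also apply to restarting study medication after recurrent stroke".

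The mRS 1-2 and mRS 3 cells each contain two sentences that use different time origins:

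- Earliest start: "3-5 days after most recent stroke onset" for mRS 1-2 and "5-7 days after most recent stroke onset" for mRS 3.
- Waiver, identical in both cells: "Brain re-imaging is not required if starting study medication more than 10 days after index stroke".

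Footnote 1 is attached to the start-time line in both cells and makes the scan mandatory: "If starting study medication within 10 days of most recent stroke in patients with mRS of 1, 2, or 3, re-imaging of the brain" is needed to rule out bleeding. Section 4.2.1 gives the restart rule in its own words: "If restarting study medication within 10 days of stroke in patients with mRS of 1, 2 or 3, re-imaging is required".

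Flow Chart footnote 19 opens with both situations ("Recommendations on timing of starting study medication after index stroke and recurrent stroke are provided in" Table 4.1.4: 1). It then requires repeat imaging for patients who initiate study drug within 10 days of the index event, and does not mention restart.

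**The concern.** The start-time line, footnote 1 and the waiver all concern the same decision, yet the waiver runs on a different clock. For a first start there is only one stroke to count from, so nothing goes wrong. After a recurrence the index stroke may be weeks or years in the past. The cell then says that no scan is needed, at the very time when footnote 1 and section 4.2.1 say that one is.

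The scan is there to detect bleeding into the brain before blinded dabigatran or ASA is given soon after a stroke. A site that works from the table cell alone could omit it. This is a matter of patient safety and clear site instructions. It does not affect the endpoint, the event count, the power or the Cox model.

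**Working it through.** The plan gives no figure to reproduce. The check is to put the two rules on a common time scale.

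**Inputs.** Both rules are from section 4.1.4, with the restart rule repeated in section 4.2.1. The threshold is 10 days in each. The earliest start is 3-5 days (mRS 1-2) or 5-7 days (mRS 3) after the most recent stroke.

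**Notation.** Let *d* be the days from index stroke to recurrence and *r* the days from recurrence to restart. The restart then falls *d + r* days after the index stroke.

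**Rules for a restart.**

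- Footnote 1 and section 4.2.1: scan required if *r* ≤ 10.
- Table cell, read literally: scan not required if *d + r* > 10.

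**Conflict.** Both hold when *r* ≤ 10 and *d* > 10 − *r*. In whole days:

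| Restart on day *r* after recurrence | Texts conflict once *d* is at least |
|---|---|
| 3 | 8 |
| 5 | 6 |
| 7 | 4 |
| 10 | 1 |

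Once *d* exceeds 10, every restart with *r* ≤ 10 is in conflict. All the recommended earliest start times (3 to 7 days) lie inside that window.

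**Example (assumed days).** Index stroke on day 0, recurrence on day 100, mRS 2, restart on day 104. The cell gives 104 > 10, so no scan. Footnote 1 gives 4 ≤ 10, so a scan is required.

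**Direction.** The opposite conflict would need *r* > 10 with *d + r* ≤ 10, which is impossible because *d* cannot be negative. The cell therefore errs only by waiving a required scan, never by demanding an extra one.

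**First start.** With no recurrence, *d* = 0 and both clocks read *r*. The rules are then complementary and agree.

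**How common is *d* > 10?** Section 3.3.2 allows randomization up to 3 months after the index stroke, or 6 months in selected patients. Protocol Table 7.6: 1 expects 193 of 353 events in the first 6 months after randomization, which leaves 353 − 193 = 160 later ones, all necessarily more than 10 days after the index stroke. This shows that *d* > 10 is the usual case. It is not a count of affected patients: it includes hemorrhagic and fatal strokes and patients who never restart. The documents do not say how many patients restart within 10 days of a recurrence.

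**The case against.** **The waiver may be meant for the first start only.** It names the index stroke, so on this reading it is silent on restart and footnote 1 governs. That would remove the conflict, and it may be how a careful reader resolves it. But nothing in the cell limits the sentence to a first start. The table's title and left-hand column cover both uses, and the line directly above was worded for both. Footnote 1 itself uses the word starting for a clock that runs from the most recent stroke.

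**The correct rule is close at hand.** Footnote 1 is marked in both cells, and section 4.2.1, written for exactly this situation, states the rule and points to that footnote. This stands, and it limits the likely harm. Section 4.2.1 says only stroke, without most recent, but in a paragraph about restart after recurrence the meaning is clear.

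**Hemorrhage has to be excluded anyway.** Section 4.2.1 requires, with no time limit, that brain hemorrhage be ruled out before any restart. A reader might infer from the cell that patients could be restarted with no bleeding check at all; that sentence shows otherwise. It does not replace the repeat scan, because it does not say when the excluding scan must be done, and a site could rely on the one taken at stroke onset. For index strokes, section 2.3 gives the purpose of re-imaging as finding bleeding missed at onset.

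**Flow Chart footnote 19.** A reader might count this as a third contradiction. The text does not support that. The footnote waives nothing; it states a requirement for initiation, for which the index event is the right clock, and it sends the reader to the table for timing. It omits restart although its first sentence names recurrent stroke, which is a gap and not a conflict. Nor should anything be inferred from the position of the marks in the Flow Chart's re-imaging row, since the column layout of that row cannot be relied on.

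**Conclusion.** The inconsistency is real and lies wholly within the current text: one sentence, repeated in two cells, uses the wrong time origin for one of the table's two stated uses. Read literally, it waives re-imaging that footnote 1 and section 4.2.1 require, whenever restart falls within 10 days of a recurrence and more than 10 days after the index stroke.

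The point is minor. It is a drafting error in a safety instruction and not a flaw in the design, since footnote 1 and section 4.2.1 show what was intended. No patient count can be given. The conclusion assumes that the waiver sentence applies to both uses of the table, as its title says, and that the stroke in the restart rule of section 4.2.1 is the recurrent one.

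**What to change.** In the mRS 1-2 and mRS 3 cells of Table 4.1.4: 1, change *index stroke* to *most recent stroke* in the waiver sentence. The cell then waives the scan when *r* > 10 and footnote 1 requires it when *r* ≤ 10, so the two are complementary for first start and restart alike.

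Optionally, for consistency, add to Flow Chart footnote 19 that restart within 10 days of a recurrent stroke also requires repeat imaging, and keep its sentence that index-stroke imaging precedes randomization. The index-only statements in sections 2.3, 6.2.1 and 6.2.2 concern randomization and can stay.

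The cost is a wording correction in two places, or three with the option. It adds no procedure, visit or patient, because the scan is already required.

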4.1.5 Blinding and procedures for unblinding

4.1.5.1 Blinding

Trial medication will be identified by a medication code number. Packaging and labelling will be otherwise identical. Interactive Response Technology will be used to assign patients to treatment groups at the start of treatment (see [Section 4.1.2](#)) and for appropriate re-supply of medication to patients throughout the duration of the trial. The IRT will also handle any required dose adjustments.

Colour, size and shape of the tablets and capsules (whether active or placebo) are identical (see [Section 4.1.1](#) for actual sizes of each unit strength dose). These measures will ensure that the medication blind will be maintained for both patient and Investigator throughout the trial.

The randomisation schedule will be generated using validated software and will be verified by a statistician who is not involved in the trial. Individuals involved in the conduct and assessments of the trial will remain blinded to the randomisation schedule until the entire database is locked.

Randomisation codes will be accessible for any authorised person at the study site via IRT. The codes should be broken only if knowledge of the patient's treatment group is needed in order to provide appropriate medical care to that patient. Refer to [Section 4.1.5.2](#) for rules of breaking the code for an individual or for all patients. The DMC will also be given access to unblinded patient information if required.

Refer to the DMC charter (available separately) for information about management of blinded information for the purposes of DMC review.

The randomization codes may be provided to bioanalytics (or designee) prior to last patient out (LPO) to allow them to exclude PK samples and assay validation samples taken from patients assigned to ASA from these analyses. Bioanalytics (or designee) will not disclose the randomization code or the results of their measurements until the study is officially unblinded.

Due to the requirement to include unblinded information in suspected unexpected serious adverse reaction (SUSAR) reports, SUSAR reports will be blinded prior to distribution to sites and trial team to ensure that the BI personnel other than the drug safety representative remains blind to treatment allocation until after database lock.

